### **2.8.1.1 Serious adverse event**

Serious adverse events will be summarized by presenting, for each treatment group, the number and percentage of patients having at least one SAE, having an SAE in each primary system organ class and having each individual AE (preferred term). For SAEs occurred during screening a listing will be prepared for all patients screened including screening failures.

### **2.8.1.2 Adverse events of special interest (AESIs)**

- The following events will be considered as adverse events of special interest:
- Infection and infestations
- Mood disorder/ depression
- Inflammatory bowel disease

The crude rates and exposure-adjusted incidence rates for AESIs will be summarized.

Important note: For the evaluation of AESIs risks primary and secondary system organ classes of the MedDRA dictionary will be considered.

Specific groupings of AESI will be considered and the number of patients with at least one event in each grouping will be reported. Such groups consist of adverse events for which there is a specific clinical interest in connection with secukinumab or adverse events, which are similar in nature (although not identical). Note that certain adverse events may be reported within multiple groupings.

All AESI groupings are defined through the use of PT, high level terms (HLT), SOC, SMQ, NMQ or through a combination of these components.

The AESI search table will be used to map reported adverse events to the notable adverse events groupings. The list of adverse events of special interest may be updated during the course of the trial based on accumulating safety data. Therefore, the clinical study report will list the AE groupings used and provide a listing of the corresponding AESI search table.

### **2.8.2 Deaths**

Deaths will be separately summarized by treatment group and overall on the safety set. Also, listing of deaths will be provided on safety set.

### **2.8.3 Laboratory data**

The summary of laboratory evaluations will be presented for three groups of laboratory tests (hematology, chemistry and urinalysis).

In addition to the individual laboratory parameters the ratios “total cholesterol / HDL” and “apolipoprotein B / apolipoprotein A1” will be derived and summarized.

## **Hematology**

The following hematology variables will be analyzed :

- Hemoglobin,
- hematocrit,
- red blood cell count,
- white blood cell count with differential counts, and
- platelet count.

## **Chemistry**

Serum chemistries will include

- glucose,
- urea,
- creatinine,
- total bilirubin,
- AST (SGOT),
- ALT (SGPT),
- GGT,
- alkaline phosphatase,
- sodium,
- potassium,
- bicarbonate,
- calcium,
- phosphorous,
- total protein,
- albumin, and
- uric acid.

For urinalysis, frequency tables will be presented.

Descriptive summary statistics for the change from baseline to each study visit will be presented. These descriptive summaries will be presented by laboratory test and treatment group. Change from baseline will only be summarized for patients with both baseline and post baseline values and will be calculated as:

$$\text{change from baseline} = \text{post baseline value} - \text{baseline value}$$

For each parameter, the maximum change from baseline within each study period will be analyzed analogously.

In addition, shift tables will be provided for all parameters to compare a patient's baseline laboratory evaluation relative to the visit's observed value. For the shift tables, the normal laboratory ranges will be used to evaluate whether a particular laboratory test value was normal, low, or high. The shifts to the most extreme laboratory test value within a treatment period will be presented (including category "high and low"). These summaries will be presented by laboratory test and treatment group.

The following laboratory parameters will be analyzed with respect to numerical Common Terminology Criteria for Adverse Events (CTCAE) grades, given in Table 2.8-1: hemoglobin, platelets, white blood cell count, neutrophils, lymphocytes, creatinine, total bilirubin (TBL), gamma-glutamyl transferase (GGT), alanine aminotransferase (ALT), aspartate aminotransferase (AST), alkaline phosphatase (ALP), glucose, cholesterol, triglycerides (TG).

These summaries will be split into hematology and chemistry for study level reports and the pooled summary of clinical safety.

**Table 2.8-1 CTCAE grades for laboratory parameters to be analyzed**

CTCAE Term	Grade 1	Grade 2	Grade 3	Grade 4
HGB decreased (Anemia)	<LLN - 100 g/L	<100 - 80 g/L	<80 g/L	
Platelet count decreased	<LLN - 75.0 x10e9 /L	<75.0 - 50.0 x10e9 /L	<50.0 - 25.0 x10e9 /L	<25.0 x 10e9 /L
White blood cell decreased	<LLN - 3.0 x 10e9 /L	<3.0 - 2.0 x 10e9 /L	<2.0 - 1.0 x 10e9 /L	<1.0 x 10e9 /L
Neutrophil count decreased	<LLN - 1.5 x 10e9 /L	<1.5 - 1.0 x 10e9 /L	<1.0 - 0.5 x 10e9 /L	<0.5 x 10e9 /L
Lymphocyte count decreased	<LLN - 0.8 x 10e9 /L	<0.8 - 0.5 x 10e9 /L	<0.5 - 0.2 x 10e9 /L	<0.2 x 10e9 /L
Creatinine increased*	>1 - 1.5 x baseline; >ULN - 1.5 x ULN	baseline; >1.5 - 3.0 x ULN	>3.0 baseline; >3.0 - 6.0 x ULN	>6.0 x ULN
TBL increased	>ULN - 1.5 x ULN	>1.5 - 3.0 x ULN	>3.0 - 10.0 x ULN	>10.0 x ULN
GGT increased	>ULN - 2.5 x ULN	>2.5 - 5.0 x ULN	>5.0 - 20.0 x ULN	>20.0 x ULN
ALT increased	>ULN - 3.0 x ULN	>3.0 - 5.0 x ULN	>5.0 - 20.0 x ULN	>20.0 x ULN
AST increased	>ULN - 3.0 x ULN	>3.0 - 5.0 x ULN	>5.0 - 20.0 x ULN	>20.0 x ULN
ALP increased	>ULN - 2.5 x ULN	>2.5 - 5.0 x ULN	>5.0 - 20.0 x ULN	>20.0 x ULN
Glucose increased (Hyperglycemia)	>ULN - 8.9 mmol/L	>8.9 - 13.9 mmol/L	>13.9 - 27.8 mmol/L	>27.8 mmol/L
Glucose decreased (Hypoglycemia)	<LLN - 3.0 mmol/L	<3.0 - 2.2 mmol/L	<2.2 - 1.7 mmol/L	<1.7 mmol/L

		>7.75 - 10.34		
Cholesterol high	>ULN - 7.75 mmol/L	mmol/L	>10.34 - 12.92 mmol/L	>12.92 mmol/L
Hypertriglyceridemia	1.71 - 3.42 mmol/L	>3.42 - 5.7mmol/L	>5.7 - 11.4 mmol/L	>11.4 mmol/L

\*Note: for “creatinine increased” the baseline criteria do not apply

Shift tables will be presented comparing baseline laboratory result (CTCAE grade) with the worst results (expressed in CTCAE grade) during the treatment phase (either initial or entire) analyzed. Of note, baseline will be defined as last assessment prior to first dosing in initial treatment phase. Patients with abnormal laboratory values will be listed and values outside the normal ranges will be flagged.

Summaries for newly occurring or worsening clinically notable lipid abnormalities will also be provided cumulatively for each of the following parameters and categories:

- HDL:
  - $\leq$ LLN
  - $<0.8 \times$  LLN
- LDL, cholesterol, triglycerides:
  - $\geq$ ULN
  - $>1.5 \times$  ULN
  - $>2.5 \times$  ULN

Newly occurring or worsening liver enzyme abnormalities will also be summarized based on the event criteria given in Table 2.8-3 below:

**Table 2.8-2 Liver-related events**

Parameter	Criterion
ALT	$>3 \times$ ULN; $>5 \times$ ULN; $>8 \times$ ULN; $>10 \times$ ULN; $>20 \times$ ULN
AST	$>3 \times$ ULN; $>5 \times$ ULN; $>8 \times$ ULN; $>10 \times$ ULN; $>20 \times$ ULN
ALT or AST	$>3 \times$ ULN; $>5 \times$ ULN; $>8 \times$ ULN; $>10 \times$ ULN; $>20 \times$ ULN
TBL	$>1.5 \times$ ULN, $>2 \times$ ULN, $>3 \times$ ULN,
ALP	$>2 \times$ ULN, $>3 \times$ ULN, $>5 \times$ ULN
ALT or AST & TBL	ALT or AST $>3 \times$ ULN & TBL $>2 \times$ ULN; ALT or AST $>5 \times$ ULN & TBL $>2 \times$ ULN; ALT or AST $>8 \times$ ULN & TBL $>2 \times$ ULN; ALT or AST $>10 \times$ ULN & TBL $>2 \times$ ULN
ALP & TBL	ALP $>3 \times$ ULN & TBL $>2 \times$ ULN ALP $>5 \times$ ULN & TBL $>2 \times$ ULN
ALT or AST & TBL & ALP	ALT or AST $>3 \times$ ULN & TBL $>2 \times$ ULN & ALP $<2 \times$ ULN (Hy’s Law) Note: elevated ALP may suggest obstruction as a consequence of gall bladder or bile duct disease; ALP may also be increased in malignancy. FDA therefore terms Hy’s Law cases as indicators of pure hepatocellular injury. This does not mean that cases of ALT or AST $>3 \times$ ULN & TBL $>2 \times$ ULN & ALP $\geq 2 \times$ ULN may not result in severe DILI.

Notes:

In studies which enroll patients with pre-existing liver disease, baseline LFT may be increased above ULN; in such a case it is meaningful to add the condition “and worse than baseline” to the abnormality

---

---

Criteria

---

---

For a combined criterion to be fulfilled, all conditions have to be fulfilled on the same visit.

The criteria are not mutually exclusive, e.g. a subject with ALT = 6.42xULN is counted for ALT >3xULN and ALT >5x ULN.

Individual subject data listings will be provided for patients with abnormal laboratory data.

Data of patients with newly occurring or worsening liver enzyme abnormalities will be listed in an additional listing.

### **HLA-B27**

Human Leukocyte Antigen-B27 (HLA-B27) will be summarized at baseline and also listing will be provided.

## **2.8.4 Other safety data**

### **2.8.4.1 ECG and cardiac imaging data**

Not applicable.

### **2.8.4.2 Vital signs**

Analysis in vital signs measurement using descriptive summary statistics for the change from baseline for each post-baseline visit will be performed. These descriptive summaries will be presented by vital sign (sitting SBP, DBP (mmHg) and pulse (beats/min)) and treatment group. Change from baseline will only be summarized for patients with both baseline and post-baseline values and will be calculated as:

change from baseline = post-baseline value – baseline value.

### **2.8.4.3 Urine pregnancy test**

Descriptive summaries using number and percentages and listings will be provided for urine pregnancy results (positive, negative) by visit for each treatment period.

## **2.9 Pharmacokinetic endpoints**

Not applicable.

## **2.10 PD and PK/PD analyses**

Not applicable.

## **2.11 Patient-reported outcomes**

Variables related to health-related quality of life (HR-QoL) are described below. All HR-QoL variables will be evaluated based on FAS patients.

### **ASAS Health Index and environmental factors related to ASAS HI**

The ASAS Health Index (ASAS HI) is an index that measures an individual's status of functioning, disability and health in individuals and is designed specifically for spondyloarthritis patients. (ASAS HI) (12).

The ASAS health index is a linear composite measure and contains 17 items (dichotomous response option: "I agree" and "I do not agree").

Each statement on the ASAS Health Index is given a score of 1 = I agree OR 0 = I do not agree. All item scores are summed up to give a total score that ranges from 0 (good functioning) to 17 (poor functioning).

Summary of ASAS Health Index and environmental factors related to ASAS HI scores will be presented.

### **Bath Ankylosing Spondylitis Functional Index (BASFI)**

The BASFI is a set of 10 questions designed to determine the degree of functional limitation in those patients with AS. The ten questions were chosen with major input from patients with AS. The first 8 questions consider activities related to functional anatomy. The final 2 questions assess the patients' ability to cope with everyday life. A 0 through 10 scale (captured by a continuous VAS) is used to answer the questions. The mean of the ten scales gives the BASFI score – a value between 0 and 10.

Frequency of BASFI response along with the summary of BASFI score will be presented.

### **Bath Ankylosing Spondylitis Disease Activity Index (BASDAI)**

The BASDAI consists of a 0 through 10 scale (0 being no problem and 10 being the worst problem, captured as a continuous VAS), which is used to answer 6 questions pertaining to the 5 major symptoms of AS:

1. Fatigue
2. Spinal pain
3. Joint pain / swelling
4. Areas of localized tenderness (called enthesitis, or inflammation of tendons and ligaments)
5. Morning stiffness duration
6. Morning stiffness severity

To give each symptom equal weighting, the mean (average) of the two scores relating to morning stiffness is taken (questions 5 and 6). The resulting 0 to 10 score is added to the scores from questions 1-4. The resulting 0 to 50 score is divided by 5 to give a final 0–10 BASDAI score. Scores of 4 or greater suggest suboptimal control of disease, and patients with scores of 4 or greater are usually good candidates for either a change in their medical therapy or for enrollment in clinical trials evaluating new drug therapies directed at AS.

For analysis of BASDAI refer to [section 2.7.2](#)

### **SF-36 Health Survey**

The Short Form Health Survey (SF-36) is a widely used and extensively studied instrument to measure health-related quality of life among healthy subjects and patients with acute and chronic conditions. It consists of eight subscales that can be scored individually: Physical Functioning, Role-Physical, Bodily Pain, General Health, Vitality, Social Functioning, Role-Emotional, and Mental Health. Two overall summary scores, the Physical Component Summary (PCS) and the Mental Component Summary (MCS) also can be computed. The SF-36 has proven useful in monitoring general and specific populations, comparing the relative burden of different disease, differentiating the health benefits produced by different treatments, and in screening individual patients.

For analysis of SF-36 refer to [section 2.7.2](#)

## 2.12 Biomarkers

Not applicable.

## 2.13 Other Exploratory analyses

All the exploratory efficacy evaluation will be performed on FAS population. Refer to [Table 1.2-1](#) of Section 1 for the list of exploratory endpoints.

The following exploratory efficacy variables will be summarized on the FAS for all applicable analysis visits unless otherwise specified.

1. Total ASAS-NSAID [Area Under Curve (AUC)] Score from treatment start with Secukinumab to a Secukinumab exposure of 12 weeks.
2. Total ASAS-NSAID [Area Under Curve (AUC)] Score From Week 4 to Week 16
3. Proportion of patients with no NSAID intake after Secukinumab exposure of 12 weeks
4. Proportion of patients with no NSAID intake at week 12.
5. Change from Baseline in the ASAS Health Index after Secukinumab exposure of 12 weeks
6. Change from Baseline in the ASAS Health Index at week 12
7. Change from baseline in BASMI
8. ASAS40 response
9. ASAS20 response
10. ASAS5/6 response
11. Change from baseline in hsCRP
12. Change from baseline in total BASDAI
13. BASDAI 50 response

14. ASAS partial remission
15. Change from baseline in ASAS components including:
  - Patient global disease activity
  - Total spinal pain
  - Inflammation (average of BASDAI questions 5 and 6)
  - BASFI
16. Change from baseline in ASDAS-CRP and ASDAS-ESR
17. ASDAS inactive disease as defined by  $ASDAS < 1.3$
18. ASDAS clinically important improvement (change in  $ASDAS \geq 1.1$ ) and major improvement (change in  $ASDAS \geq 2.0$ )
19. Reasons given in the patient diary on why he was not able to taper NSAIDs despite reduced spinal pain

All endpoints relating to exploratory objectives will be summarized descriptively. Summary statistics will include absolute frequencies and percentages for the categorical variables and the number of patients (n), minimum, mean, median and maximum for continuous variables. Change from baseline will also be presented for some exploratory variables based on the the endpoints mentioned in section 1 Table 1.2-1. Graphical representation will also be performed if required.

The following exploratory endpoints will also be summarized categorically as absolute and relative frequencies (proportions, %).

- Proportion of patients fulfilling ASAS20 criteria at week 4 for secukinumab 150 mg s.c. (delayed tapering) vs. week 20 in patients switching from placebo after weeks of secukinumab exposure.
- Proportion of patients with no NSAID intake at week 12 for secukinumab 150 mg s.c. (delayed tapering) and at week 16 for secukinumab 150 mg s.c. (early tapering).
- Proportion of patients with no NSAID intake at week 12 for each treatment arm.
- Proportion of patients fulfilling the ASAS40 criteria in each treatment group over time.
- Proportion of patients fulfilling the ASAS20 criteria in each treatment group over time.
- Proportion of patients fulfilling the ASAS5/6 criteria in each treatment group over time.
- Proportion of patients fulfilling BASDAI 50 response criteria in each treatment group over time.
- Proportion of patients fulfilling ASAS partial remission criteria in each treatment group over time.
- Proportion of patients with ASDAS inactive disease (i.e  $ASDAS < 1.3$ ).
- Proportion of patients with ASDAS clinically important improvement (change in  $ASDAS \geq 1.1$ ) and major improvement (change in  $ASDAS \geq 2.0$ ).

- Proportion of patients for each reason given in the patient diary on why he was not able to taper NSAIDs despite reduced spinal pain.
- Proportion of patients fulfilling ASAS20 criteria in the pooled Secukinumab groups after exposure of 12 weeks (i.e. Secukinumab delayed tapering at week 12 and Secukinumab early tapering at week 16) and placebo regimen at Week 12.
- Proportion of patients fulfilling ASAS20 criteria in the pooled Secukinumab groups after exposure of 12 weeks (i.e. Secukinumab delayed tapering at week 12 and Secukinumab early tapering at week 16) and placebo regimen at Week 16.
- Total ASAS-NSAID score in the pooled Secukinumab groups after exposure of 12 weeks (i.e. Secukinumab delayed tapering at week 12 and Secukinumab early tapering at week 16) and placebo regimen at Week 12.
- Total ASAS-NSAID score in the pooled Secukinumab groups after exposure of 12 weeks (i.e. Secukinumab delayed tapering at week 12 and Secukinumab early tapering at week 16) and placebo regimen at Week 16.

Total BASDAI, BASDAI question 1 and question 2 and ASAS-NSAID score (each in Y-axis) compared to time (X-axis) will be presented graphically.

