Response at Week 16 to ASAS20 for Secukinumab (early-tapering) versus placebo will be evaluated using a logistic regression model with treatment as a factor and baseline weight as a covariate.

ASAS-NSAID at Week 12

Between-treatment differences in the change in ASAS-NSAID relative to baseline will be evaluated using a mixed-effect model repeated measures (MMRM). Treatment group and analysis visit as factors, baseline ASAS-NSAID and weight as continuous covariates. Treatment by analysis visit and baseline ASAS-NSAID by analysis visit will be included as interaction terms in the model. An unstructured covariance structure will be assumed for the model. The significance of the Secukinumab pooled treatment effect will be determined from a linear contrast comparing the (mean of the) two Secukinumab regimens to placebo. The significance of the two individual Secukinumab treatment group effects will be determined from the pairwise comparisons performed between Secukinumab regimens and placebo.

BASDAI at Week 12/16

The change from baseline to Week 12/16 in total BASDAI will be analyzed using a MMRM with treatment regimen and analysis visit as factors and weight and baseline score as continuous covariates. Treatment by analysis visit and baseline by analysis visit will be included as interaction terms in the model. An unstructured covariance structure will be assumed for this model. The significance of the Secukinumab treatment effect will be determined from the pairwise comparisons performed between Secukinumab regimens and placebo.

Other secondary variables

SF-36 PCS

For the change in SF-36 PCS, between-treatment differences will be evaluated using a mixed effect repeated measures model (MMRM). Treatment group and analysis visit will be included as categorical factors and baseline SF-36 PCS score and weight as continuous covariates. Treatment by analysis visit and baseline SF-36 PCS score by analysis visit will be included as interaction terms in the model. An unstructured covariance structure will be assumed for the model. The significance of the Secukinumab treatment effect will be determined from the pairwise comparisons performed between Secukinumab regimens and placebo.

Between-treatment comparisons for binary variables in the FAS population (e.g. ASAS20) at individual analysis visits will be evaluated using a logistic regression model with treatment as a factor and weight as a covariate for any analysis up to end of study.

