Continuous variables (e.g. change from baseline in BASDAI question 2) will be evaluated using a MMRM with treatment regimen and analysis visit as factors and weight and baseline score as continuous covariates. Treatment by analysis visit and baseline by analysis visit will be included as interaction terms in the model. An unstructured covariance structure will be assumed for this model. The significance of the treatment effects for Secukinumab regimens at different analysis visits will be determined from the pairwise comparisons performed between Secukinumab regimens and placebo and/or Secukinumab at the appropriate analysis visits.

9.5.2 **Exploratory efficacy variables**

The exploratory efficacy variables are listed below. Exploratory efficacy variables will be analyzed using the FAS population.

- Total ASAS-NSAID [Area Under Curve (AUC)] Score from treatment start with Secukinumab to a Secukinumab exposure of 12 weeks.
- Total ASAS-NSAID [Area Under Curve (AUC)] Score From Week 4 to Week 16
- Proportion of patients with no NSAID intake after Secukinumab exposure of 12 weeks
- Proportion of patients with no NSAID intake at week 12.
- Change from Baseline in the ASAS Health Index after Secukinumab exposure of 12 weeks
- Change from Baseline in the ASAS Health Index at week 12
- Change from baseline in BASMI
- ASAS40 response
- ASAS20 response
- ASAS5/6 response
- Change from baseline in hsCRP
- Change from baseline in total BASDAI
- BASDAI 50 response
- ASAS partial remission
- Change from baseline in ASAS components including:
 - a. Patient global disease activity
 - b. Total spinal pain
 - c. Inflammation (average of BASDAI questions 5 and 6)
 - d. BASFI
- Change from baseline in ASDAS-CRP and ASDAS-ESR
- ASDAS inactive disease as defined by ASDAS < 1.3
- ASDAS clinically important improvement (change in ASDAS ≥ 1.1) and major improvement (change in ASDAS ≥ 2.0)
- Reasons given in the patient diary on why he was not able to taper NSAIDs despite reduced spinal pain

Secukinumab groups at week 12 (delayed tapering) and week 16 (early tapering) will be compared for all primary, secondary and exploratory variables that have not been outlined. Variables such as hsCRP whose distribution is not anticipated to be normal will be transformed and analyzed on the loge scale. All other details and analyses regarding the exploratory efficacy variables will be outlined in the statistical analysis plan.

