
To demonstrate that the efficacy of Secukinumab 150 mg s.c. at week 12 is superior to placebo based on the change from baseline in health-related Quality of Life as measured by the SF-36 PCS.
	
Mean change from baseline in SF-36 PCS in the pooled Secukinumab groups (i.e. Secukinumab delayed tapering and Secukinumab early tapering) and placebo regimen at Week 12.

To demonstrate that the efficacy of Secukinumab 150 mg s.c. (Secukinumab from week 0 with NSAID tapering allowed from week 4; “delayed tapering”) at Week 12 is superior to placebo based on the change from baseline in health-related Quality of Life as measured by the SF-36 PCS.
	
Mean change from baseline in SF-36 PCS for Secukinumab (delayed tapering) and placebo regimen at Week 12.

To demonstrate that the efficacy of Secukinumab 150 mg s.c. (Secukinumab from week 4 with NSAID tapering allowed from week 4; “early tapering”) at Week 12 is superior to placebo based on the change from baseline in health-related Quality of Life as measured by the SF-36 PCS.
	
Mean change from baseline in SF-36 PCS for Secukinumab (early tapering) and placebo regimen at Week 12.

To compare between both Secukinumab regimens concerning the change from baseline in ASAS-NSAID score after 12 weeks of Secukinumab exposure (ASAS-NSAID index at Week 12 for “delayed tapering” vs. Week 16 for “early tapering”).
	
Mean change from baseline in total ASAS-NSAID score after 12 weeks of Secukinumab exposure (ASAS-NSAID index at Week 12 for “delayed tapering” vs. Week 16 for “early tapering”).

Exploratory objective
	

To compare between both Secukinumab regimens concerning the change from baseline in the BASDAI after 12 weeks of Secukinumab exposure (BASDAI at Week 12 for “delayed tapering” vs. Week 16 for “early tapering”).
	
Mean change from baseline in the BASDAI after 12 weeks of Secukinumab exposure (BASDAI at Week 12 for “delayed tapering” vs. Week 16 for “early tapering”).

To evaluate change in patient reported neck, back and hip pain (BASDAI question 2) beginning from Secukinumab treatment on a continuous basis in patients exposed to Secukinumab 150 mg s.c. for 12 weeks vs. placebo.
	
Mean change in patient reported neck, back and hip pain score (BASDAI question 2) from baseline at Week 12 for secukinumab 150 mg s.c. (delayed tapering) vs. placebo.  Mean change in patient reported neck, back and hip pain score from baseline at week 16 for

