##### **2.7.1 Secondary endpoints**

The secondary efficacy variables are listed below. Secondary efficacy variables will be analyzed using the FAS population.

- ASAS20 response at Week 12/16.
- ASAS-NSAID response at Week 12.
- Change from baseline in BASDAI at Week 12/16.
- Change from baseline in SF36 physical component score at Week 12/16.
- Change from baseline in ASAS-NSAID score at Week 12 for Secukinumab (delayed tapering) vs. change from baseline in ASAS-NSAID score at Week 16 for Secukinumab (early tapering)
- Change from baseline in BASDAI at Week 12 for Secukinumab (delayed tapering) vs change from baseline in BASDAI at Week 16 for Secukinumab (early tapering).
- Change from baseline in BASDAI question 2
- ASAS20 response at Week 4 for Secukinumab (delayed tapering) vs. ASAS20 response at Week 20 for placebo group

Please refer to the main definition section.

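### The SAP commits to no adjusted difference or confidence interval for early versus delayed tapering on BASDAI, and contradicts itself and the protocol on how that comparison and BASDAI question 2 are analysed

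*SAP*

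**What the plan says.** **Class.** Protocol 9.5.1 and SAP 2.7.1 both list two items among the secondary variables: the BASDAI comparison of delayed tapering (Week 12) with early tapering (Week 16), and change from baseline in BASDAI question 2. Protocol 2.3 and SAP Table 1.2-1 place both under exploratory objectives. The table's endpoint for the first is "Mean change from baseline in the BASDAI after 12 weeks of Secukinumab exposure".

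**Method in the protocol.** After the models for named endpoints, Protocol 9.5.1 has a general paragraph: "Continuous variables (e.g. change from baseline in BASDAI question 2) will be evaluated using a MMRM". It takes significance from "pairwise comparisons performed between Secukinumab regimens and placebo and/or Secukinumab at the appropriate analysis visits". This is the only place in the protocol where an MMRM contrast between the two secukinumab regimens is stated.

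**Method in the SAP.** The part of SAP 2.7.2 on other secondary variables stops at SF-36 PCS, so the general paragraph is absent. The BASDAI MMRM in 2.7.2 promises an adjusted mean difference with a 95% interval and p-value, but names only regimen-versus-placebo comparisons. The contrasts described in the text of 5.4 are also against placebo or control. SAP 2.13 states: "All endpoints relating to exploratory objectives will be summarized descriptively", with "the number of patients (n), minimum, mean, median and maximum for continuous variables". Section 4, on changes to the protocol's analyses, is marked not applicable.

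**The concern.** In the SAP the class decides the method, and these items have two classes. Read as secondary, they should be modelled. Read as exploratory, they fall under the descriptive rule of 2.13. A programmer could follow either section in good faith and produce different tables.

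When to start NSAID tapering after starting secukinumab is the reason Protocol 3.4 gives for having two active arms. If 2.13 is followed, disease activity under the two regimens is reported as separate arm summaries, without an estimated difference or its precision. Two similar means could then be taken to show that timing does not matter, when the data may be too imprecise to say so. If the model is added after unblinding, the choice of contrast and visit will no longer be clearly prespecified.

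**Working it through.** **Step 1. Follow each route through the SAP for the regimen comparison of BASDAI.**

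| Route | What it gives | Regimen difference with interval promised? |
|---|---|---|
| 2.7.1, then 2.7.2 (secondary) | BASDAI MMRM, adjusted difference, 95% CI and p-value | No: only contrasts with placebo are named |
| Table 1.2-1, then 2.13 (exploratory) | Descriptive summaries | No |
| 5.4, ANCOVA text | Intervals for secukinumab versus placebo | No |
| 5.4, mixed-model text | Contrasts with placebo; applies to key secondary variables, which 2.6 marks as not applicable | No |
| 5.4, mixed-model code | Requests all pairwise treatment-by-visit differences with confidence limits | Would be printed if run for BASDAI, but no text commits to reporting it |

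**Step 2. The same for BASDAI question 2.** SAP 2.7.2 has no model for it. The 5.4 ANCOVA, which covers continuous endpoints expected to be normally distributed, could give an interval against placebo. The 2.13 rule says descriptive. The protocol's MMRM, which names question 2 as its example, is not carried over.

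**Step 3. ASAS-NSAID.** The regimen comparison of ASAS-NSAID (Protocol 2.2, objective 14) is secondary in both documents throughout. SAP 2.7.2 names the pooled and the individual contrasts with placebo for this score, but none between regimens. The omitted general paragraph was the only text that supplied one.

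**Step 4. Does the protocol leave this to the SAP?** Protocol 9.5.2 leaves remaining details of exploratory variables to the SAP. The omitted paragraph stands in 9.5.1, under secondary variables, so the delegation does not clearly cover it. Section 4 should then have recorded the change.

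**Step 5. Precision at stake.** The plan gives no precision figure for this comparison, so there is none to reproduce. Inputs:
- about 190 patients randomised 1:1:1 (SAP 1.1), so 190/3 ≈ 63 per arm;
- BASDAI SD 2.8 and planning difference from placebo 1.8 (Protocol 9.7);
- ASAS-NSAID SD 40 (Protocol 9.7).

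Approximate 95% half-width for two independent arms = 1.96 × SD × √(2/n), with √(2/63) = 0.1782.
- BASDAI: 1.96 × 2.8 × 0.1782 = 0.98 points, which is 0.98/1.8 = 54% of the planning difference from placebo.
- ASAS-NSAID: 1.96 × 40 × 0.1782 ≈ 14.0 points.
- BASDAI question 2: the documents give no SD. Assuming 2.0 to 3.2, the half-width is about 0.70 to 1.12 points.

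These figures assume no missing data and no gain from covariate adjustment. They describe the trial's precision. They are not an effect of the defect.

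**The case against.** The strongest reply is that the SAP already provides intervals. Section 2.7.1 calls both items secondary. Neither the regimen comparison nor question 2 appears in the numbered list in 2.13; only the cross-reference to Table 1.2-1 brings them in. Section 2.11 sends BASDAI to 2.7.2, which promises an interval, and the code in 5.4 would print the regimen difference. This stands to the extent that a reader who infers that these contrasts can get no interval goes too far: that would require 2.13 to override everything else, and nothing says it does. It does not supply a commitment to report the regimen contrast.

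It can also be said that the BASDAI paragraph in Protocol 9.5.1 itself names only contrasts with placebo, so an MMRM for early versus delayed BASDAI rests on the general paragraph that follows. That is right. But the comparison is on the protocol's secondary list, and the general paragraph is the only text that can serve it.

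Three further inferences are tempting and not supported:
- That the SAP created the double classification. Protocol 2.3 and 9.5.1 already disagree, and the SAP repeats the conflict.
- That the SAP dropped a planned logistic model for early versus delayed ASAS20. The protocol's logistic sentence concerns comparisons at individual visits, not Week 12 in one arm against Week 16 in another, and this comparison is not on the 9.5.1 list.
- That no SD will be shown. The list in 2.13 omits it, but SAP 2.1 includes it for continuous data, and the list in 2.13 need not be exhaustive.

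Finally, none of these comparisons is among H1 to H11, so no confirmatory conclusion or type I error is affected. That stands and limits the weight of the point.

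**Conclusion.** The point holds as an inconsistency with a practical consequence. The SAP gives the same items two classes with different methods, omits a protocol model without declaring it, and commits nowhere to a difference or interval between the regimens. The accurate statement is that no interval is assured.

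At the planning SD and about 63 per arm, an observed BASDAI difference of zero would still be compatible with true differences of up to about 0.98 points either way, under the assumptions in the working. That is the information a reader needs in order not to take similar means as evidence of similar effect. The sponsor should correct this before unblinding. It does not threaten the primary or the hierarchical analyses.

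**What to change.** 1. Give the regimen comparison of BASDAI and BASDAI question 2 one class each, the same in Protocol 2.3 and 9.5.1 and in SAP Table 1.2-1 and 2.7.1.
2. Restore the protocol's general MMRM paragraph in SAP 2.7.2, with these contrasts written out, each as an adjusted mean difference with a 95% interval and stated to lie outside H1 to H11:
   - delayed tapering at Week 12 minus early tapering at Week 16, for BASDAI;
   - the same contrast for ASAS-NSAID (secondary objective 14);
   - the question 2 contrasts already described in Table 1.2-1.
3. In SAP 2.13, except these items from the descriptive rule. As a minor tidy-up, align its summary list with SAP 2.1 by adding the SD.
4. If the sponsor prefers descriptive reporting, declare it with a reason in SAP section 4. This removes the undeclared departure but leaves the regimen comparison without a measure of precision, so it is the weaker option.

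The cost is wording and a few table cells. No new data and no alpha are needed. The mixed-model code in 5.4 already requests the treatment-by-visit differences with limits, so each regimen contrast is one line of its output for an endpoint run through that model.
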